2.4 Endpoints

The endpoints are:

- Characteristics of patients treated;
- Procedure for treating patients with mRCC in CR with Sunitinib (Case);
- Adverse events (AE).

The analysis of biological data and biomarkers will be the subject of a separate analysis plan.

2.5 Number of patients required

The primary objective of the study is to describe the characteristics of mRCC patients achieving a CR with Sunitinib (Cases) and to compare them to the characteristics of metastatic renal cell carcinoma patients not achieving a CR with Sunitinib to identify factors associated with the occurrence of complete remission.

A sample size of N = 40 cases and N = 80 controls will provide a power of 80% in the detection:

- For continuous variable with a normal distribution, of an effect size (Cohen's d) ≥ 0.55 ;
- For a dichotomous variable, of a frequency difference between cases and controls corresponding to the ORs presented in the table below:

Frequency in controls	10%	20%	30%	40%	50%	60%	70%	80%	90%
Odds Ratio	≥ 4.33	≥ 3.27	≤ 0.19 or ≥ 3.16	≤ 0.26 or ≥ 3.12	≤ 0.29 or ≥ 3.44	≤ 0.32 or ≥ 3.78	≤ 0.32 or ≥ 5.29	≤ 0.31	≤ 0.23

3 ANALYSIS SET

3.1 Population of active doctors

The population of doctors will include all oncologists who have included at least one patient.

3.2 Population of patients included

The patient population included will comprise patients who have signed their consent form and have completed the inclusion visit:

- The Case population will include patients with mRCC in CR (validated after the scan review) taking Sunitinib.
- The Control population will include non-CR patients with mRCC treated with first-line Sunitinib.

3.3 Population of followed-up patients

The population of followed-up patients will include all patients who have been including and who have attended at least one follow-up visit.

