6.4 Description of follow-up visits for mRCC patients in CR (Cases)

Study population: Population of followed-up patients - Cases

Patient follow-up data will be described for the cases at 12 and 24 months:

- Disease progression (Complete response / Partial response / Progression / Stabilisation / Not assessed);
- Sunitinib treatment ongoing (Yes/No);
If yes:
 - Current dose (mg/d);
 - Current regimen (4/2 / 2/1 / Continuous / Other);
A list of the other regimens will be presented.
- Temporary discontinuation of Sunitinib (Yes/No);
If yes:
 - Number of temporary discontinuations per patient
 - The temporary discontinuations will then be described (the statistical unit considered will then be the temporary discontinuation and not the patient):
 - Reason for temporary discontinuation (Progression / Intolerance / Complete response / Local treatment / Other);
A list of the other reasons will be presented.
 - Treatment resumed (Yes/No);
 - Duration of temporary discontinuation (days);
- Permanent discontinuation (Yes/No);
If yes:
 - Reason for permanent discontinuation (Progression / Intolerance / Decision of patient or doctor / Other);
A list of the other reasons will be presented.
 - Duration of treatment with Sunitinib since CR (months);

Patient follow-up data will be described for the cases at the time of the progression:

- Time between CR and progression (months);
 - Duration of additional Sunitinib treatment (pseudo-adjuvant), starting at CR (months)
 - Type of progression (Local Progression/Distant Progression);
If distant progression:
 - at which level (at a known metastatic site/new metastatic site);
 - Location of metastases:
 - Lung (Yes/ No);
 - Bones (Yes/No);
 - Liver (Yes/ No);
 - Adrenal glands (Yes/No);
 - Pancreas (Yes/No);
 - Brain (Yes/No);
-

- Lymph nodes (Yes/No);
If Lymph nodes:
 - Supra-diaphragmatic (Yes/No);
 - Sub-diaphragmatic (Yes/No);
- Recurrence at nephrectomy site (Yes/No) ;
- Other (Yes/ No);
A list of the other locations will be presented.
- Number of metastatic sites;
- Systemic treatment after progression (Yes/No)
- Description of systemic treatments after progression by type of treatment (Bevacizumab with interferon / Bevacizumab without interferon / Sunitinib restart / Sorafenib / Temsirolimus/ Everolimus / Other)
A list of the other systemic treatments will be presented.
A list of systemic treatments including daily dose will be presented.

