Patient follow-up data will be described for the cases at the end-of-study visit:

- Best objective response observed after progression (Complete / Partial / Progressive / Stabilised);
- Duration of treatment received after progression with first-line Sunitinib (months);
- Early termination of the study (Yes/No);
- Response achieved (persistent CR since inclusion visit / CR after treatment of recurrence / Disease progression);
- Number of subsequent treatment lines from progression, post CR;
- Death (Yes/ No).

Progression-free survival at the end of the study will be analysed using the Kaplan Meier method, with a presentation of the survival curve. The progression-free survival rate will be estimated with a 95% confidence interval.

6.5 Description of follow-up visits for mRCC patients treated with first-line Sunitinib, non CR (Controls)

Study population: Population of followed-up patients - Controls

Patient follow-up data will be described for the controls at 6 and 12 months of treatment:

- Sunitinib dose (50 mg / 37.5 mg / 25 mg);
- Current regimen (4/2 / 2/1 / Continuous);
- Clinical assessment (Complete Response / Partial Response / Stable Disease / Progression);
If Partial Response:
 - Percentage of tumour reduction (%)
- Location of metastases:
 - Lung (Yes/ No);
 - Bones (Yes/No);
 - Liver (Yes/ No);
 - Adrenal glands (Yes/No);
 - Pancreas (Yes/No);
 - Brain (Yes/No);
 - Lymph nodes (Yes / No); If Lymph nodes:
 - Supra-diaphragmatic (Yes/No);

- Sub-diaphragmatic (Yes/No);
- Recurrence at nephrectomy site (Yes/No) ;
- Other (Yes/ No);
A list of the other locations will be presented.
- Number of metastatic sites;

Patient follow-up data will be described for the controls at the time of the progression:

- Time between initiation of treatment and progression (in months);
- Type of progression (Local Progression/Distant Progression);
If distant progression, at which level (at a known metastatic site/new metastatic site);
- Location of metastases:
 - Lung (Yes/ No);
 - Bones (Yes/No);
 - Liver (Yes/ No);
 - Adrenal glands (Yes/No);
 - Pancreas (Yes/No);
 - Brain (Yes/No);
 - Lymph nodes (Yes / No); If Lymph nodes:
 - Supra-diaphragmatic (Yes/No);
 - Sub-diaphragmatic (Yes/No);
 - Recurrence at nephrectomy site (Yes/No) ;
 - Other (Yes/ No);
A list of the other locations will be presented.
- Number of metastatic sites;

Patient follow-up data will be described for the controls at the end-of-study visit:

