- Patients still receiving Sunitinib (Yes/No);
If yes:
 - Response (Complete Response / Partial Response / Stable Disease / Progression);
- If No:
 - Progression (Yes/ No);
 - Duration of Sunitinib treatment (months);
 - New treatments (Yes/No);
A list of new treatments will be presented.
- Number of subsequent treatment lines.
- Early termination of the study (Yes/No);
- Death (Yes/ No).

Progression-free survival at the end of the study will be analysed using the Kaplan Meier method, with a presentation of the survival curve. The progression-free survival rate will be estimated with a 95% confidence interval.

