6.6 Description of adverse events

Study population: Population of followed-up patients

The number of AEs, the number and percentage of patients with at least one AE will be described by group for the following event categories:

- All AEs by system organ class,
- All AEs likely to be related to the study drug ('Yes' or Missing response method) by system organ class,
- All serious AEs by system organ class,
- All serious AEs likely to be related to the study drug ('Yes' or Missing response method) by organ class,

The AEs will be described according to severity, action taken regarding the study treatment, and progression.

AEs reported during the study will be coded using the MedDRA dictionary, version 20.0.

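### PFS, deaths, early terminations and all adverse event tables are restricted to patients who attended a follow-up visit, so recorded outcomes of patients with no visit are left out

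*SAP*

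**What the plan says.** SAP section 3 defines two patient sets.

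- The included set (3.2) is "patients who have signed their consent form and have completed the inclusion visit", in CR on Sunitinib for Cases and on first-line Sunitinib for Controls.
- The followed-up set (3.3) adds a condition met only after entry: "The population of followed-up patients will include all patients who have been including and who have attended at least one follow-up visit".

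The second set governs three sections.

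- SAP 6.4 opens with "Study population: Population of followed-up patients - Cases".
- SAP 6.5 opens with "Study population: Population of followed-up patients - Controls".
- SAP 6.6 opens with "Study population: Population of followed-up patients" and covers all AE outputs.

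Sections 6.4 and 6.5 each contain a death row, an early-termination row and the sentence "Progression-free survival at the end of the study will be analysed using the Kaplan Meier method". None of these names another set, and no supporting analysis on the included set is planned. The SAP 6.1 layout gives the numbers included and followed up by group, but not the outcomes of those in between.

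**The concern.** Membership of the followed-up set depends on surviving and attending after inclusion, yet none of these outputs needs a visit. A patient who dies before any follow-up visit has an outcome that the plan itself defines and collects, and then does not analyse.

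For AEs, which are one of the three endpoints listed in SAP 2.4, the tables could omit fatal events. For PFS and deaths, a group's figures would describe only patients who had reached a visit. The early-termination row would miss those who left first.

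**Working it through.** **1. Are the data available without a visit?** Yes.

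- SAP 5.2 makes all-cause death without progression an uncensored PFS event at the date of death. It also derives length of follow-up from the latest of last visit, last news and death.
- The Case CRF (protocol Appendix 5) sends the site to the latest-information or death form when the 36-month visit did not take place. The Control CRF (Appendix 6) has latest-information and death fields.
- Protocol section 10 has AEs and SAEs recorded electronically. Reporting runs from first dose, or from consent if the patient is already exposed. A malignancy that is fatal in the reporting period is recorded as a Grade 5 SAE.

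**2. Is there a window for the loss?** Controls need a life expectancy of at least 3 months (protocol 8.2.4), and their first scheduled follow-up CRF page is at 6 months. Cases have an annual visit. Protocol 8.1.4 and SAP 2.3 also mention routine visits at intervals of 2 to 3 months. If those count, the window is shorter but still open.

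**3. Who is lost?** SAP 2.3 places the progression visit under follow-up visits, the titles of 6.4 and 6.5 refer to follow-up visits and both sections contain the progression data, and Annex 1 lists the progression visit. On the natural reading it counts. The loss is then mainly patients with no visit at all.

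**4. Size.** The plan gives no figure for these outputs, so there is none to reproduce. Apart from the planned 80 Controls, all inputs below are assumptions: 56 progression-free at 6 months, and no other censoring before then.

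If *k* of *N* patients die before any visit, S(included) = (1 − k/N) × S(followed-up).

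| Dropped from the 80 | 6-month PFS reported | True value |
|---|---|---|
| 1 early death | 56/79 = 70.9% | 70.0% |
| 2 early deaths | 56/78 = 71.8% | 70.0% |
| 4 early deaths | 56/76 = 73.7% | 70.0% |
| 4 event-free patients, no visit | 52/76 = 68.4% | 70.0% |

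Check on the third row: (1 − 4/80) × 73.7% = 70.0%. The 95% sampling half-width is 1.96 × √(0.70 × 0.30/80) = 10.0 points.

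The last row takes the four event-free patients as known to be event-free past 6 months, which is what the last-news row of the SAP 5.2 table gives at end of study. The 5.2 note instead censors at the last visit. For these four that is the inclusion visit, so they add no time at risk and the included-set estimate is itself 52/76 = 68.4%. The two 5.2 rules thus differ by 1.6 points on the same data.

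**5. Death row**, assuming 40 deaths among 80 Controls (50.0%):

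- 4 early deaths dropped: 36/76 = 47.4%.
- 4 early deaths and 4 living patients dropped: 36/72 = 50.0%.
- 4 living patients dropped: 40/76 = 52.6%.

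AE percentages behave in the same way, because both numerator and denominator can change.

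**The case against.** The strongest reply is that little depends on this. The primary case-control comparison (SAP 6.3) uses the included set. PFS is descriptive, belongs to no stated objective and is not a 2.4 endpoint. The number excluded can be read from the 6.1 layout, and SAEs still reach the sponsor. If routine visits count, only patients with no contact in the first 2 to 3 months are lost. The illustrated shifts are well inside sampling error. All of this stands and limits the weight of the point. It does not justify the restriction, because the exclusion remains under every reading of a follow-up visit and a better set is already defined.

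A reader might infer three stronger things that the documents do not support.

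- *Control PFS is necessarily inflated.* Dropping early deaths alone raises it, but event-free patients without a visit leave too, and the 68.4% row shows the opposite movement.
- *Early progressors are dropped as well.* The placement of the progression visit in SAP 2.3, 6.4, 6.5 and Annex 1 points the other way.
- *The Case PFS time origin is part of this fault.* The Case clock starts at a CR up to 5 years before inclusion (protocol 8.2.3), and delayed entry is a fair question. But it affects every Case whatever SAP 3.3 says, and should be a separate point.

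**Conclusion.** The point holds and should be fixed, as a limited defect in secondary and safety outputs. As written, the SAP excludes from PFS, the death and early-termination rows and all AE tables any included patient with no follow-up visit, even when the outcome is on file. That conflicts with its own PFS event definition. The AE tables matter most, because AEs are a listed endpoint.

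The direction of the net bias in PFS, death and AE percentages is not determined. The size is unknown and may be zero. With 1 to 4 early deaths assumed among 80 Controls and nobody else dropped, 6-month PFS moves by 0.9 to 3.7 points. The existence of the exclusion rests on the text of SAP 3.3 and 6.4 to 6.6. Its size rests entirely on the assumed counts.

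**What to change.** 1. Use the included population (SAP 3.2) for the 6.6 AE tables, the death and early-termination rows, and PFS in 6.4 and 6.5. Confirm that 3.2 means patients exposed to Sunitinib. If so, no separate safety set is needed.
2. Keep the followed-up set for the visit-by-visit descriptions in 6.4 and 6.5.
3. List in 3.3 which visits count as follow-up visits, with an explicit statement on routine and progression visits.
4. Apply one censoring rule to event-free patients with no visit. The 5.2 note (last visit) and the 5.2 table (last news at end of study) disagree: for a Control alive at the end they give about day 0 and about month 36. If last visit is kept, set day 0 as the floor, because the inclusion visit can precede treatment start.
5. Decide delayed entry for Case PFS separately, but before the Case curve is run on the included set. Without it, Cases with no visit would add time from CR to inclusion that they had already survived by definition.

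The cost is changed set names in three sections, one list of visits, one reconciled censoring rule and the matching program edits. No new data are needed. The reported figures may move slightly in either direction.

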4 GENERAL CONSIDERATIONS FOR THE STATISTICAL ANALYSIS OF THE DATA

4.1 Statistical methods

The biostatistics department at AXIAL will perform the statistical analysis, with the exception of the analysis of biological data and biomarkers. Data will be analysed using SAS® software (version 9.4 or later - SAS Institute, North Carolina, USA).

Statistical tests will be carried out bilaterally at a 5% significance level (alpha).

Results will be presented in the form of tables per group (Cases/Controls) presenting:

- For quantitative parameters: number of patients (n), mean and standard deviation, minima and maxima, median and quartiles, and number of missing values.
- For qualitative parameters: number of patients, absolute and relative frequencies for each parameter modality, and number of missing values. Missing data will not be considered when calculating percentages.

Quantitative parameters will be compared between groups using the following methods: Beforehand, the distribution of the parameter will be checked graphically and by using Skewness and Kurtosis and Shapiro-Wilk statistics. If the distribution is considered normal, groups will be compared using a Student's t-test and the difference in means and the 95% Confidence Interval (CI) will be presented. If this is not the case, groups will be compared using a Wilcoxon rank sum test and Hodges-Lehmann estimator, with a presentation of the 95% CI.

For non-ordinal qualitative variables, groups will be compared using the Chi-2 test (or Fisher's exact test if the theoretical numbers <5) and the odds ratio will be presented when specified.

For ordinal qualitative variables, groups will be compared using the Cochran-Mantel-Haenszel test, ridit modified scores ('row mean score differ'). For ordinal qualitative count variables, groups will be compared using the Cochran-Mantel-Haenszel test, 'row mean score differ' table option.

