2.2 Objectives of the study

2.2.1 Primary objective

The primary objective is to describe the characteristics of mRCC patients achieving a CR with Sunitinib (Cases) and compare them to the characteristics of mRCC patients not achieving a CR with Sunitinib (Controls) to identify factors associated with the occurrence of CR.

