6.3.2 Other characteristics

Study population: Population of patients included

The demographic characteristics of the patients will be described by group and compared:

- Time of diagnosis of metastatic renal cell carcinoma;
- Nephrectomy (Yes/ No)*;
If Nephrectomy:
 - Extended or partial;
 - With or without adrenalectomy;
 - With or without curettage;
 - Open or laparoscopic approach;
 - Time between diagnosis of metastatic renal cell carcinoma to nephrectomy (in months);

- Pathological classification (Clear cell carcinoma / Papillary carcinoma / Chromophobe carcinoma / Bellini duct carcinoma / Medullary carcinoma / Sarcomatoid carcinoma / Other);
A list of other classifications will be presented.
- TNM classification (T / N / M and TNM);
- Tumour size (mm);
- Furhamn nuclear grade (I / II / III / IV);
- Necrosis (Yes/ No)*;
- Pulmonary embolism (Yes/No)*;
- Sarcomatoid component (Yes/No)*.

** For these qualitative variables, the odds ratio (Case versus Control) will be presented.*

The demographic characteristics of the patients, at initiation of Sunitinib, will be described by group and compared:

- Time between diagnosis of metastatic renal cell carcinoma and initiation of Sunitinib (in months);
- Location of metastases:
 - Lung (Yes/ No);
 - Bones (Yes/No);
 - Liver (Yes/ No);
 - Adrenal glands (Yes/No);
 - Pancreas (Yes/No);
 - Brain (Yes/No);
 - Lymph nodes (Yes/No);
If Lymph nodes:
 - Supra-diaphragmatic (Yes/No);
 - Sub-diaphragmatic (Yes/No);
 - Recurrence at nephrectomy site (Yes/No) ;
 - Other (Yes/ No);
A list of the other locations will be presented.
- Number of metastatic sites;
- MSKCC prognostic classification (Good prognosis/Intermediate prognosis/Poor prognosis).

The characteristics of the patients in CR will be described for the Cases:

- Time between Sunitinib initiation and CR (years);
- Method of achieving the CR (Medical treatment alone/Combined with local treatment);
If combined:
 - Surgery (Yes/No);
 - Radiotherapy (Yes/ No);
 - Radiofrequency (Yes/ No);
 - Cryoablation (Yes/ No);
 - Metastasectomy (Yes/ No);
 - Other (Yes/ No);

A list will be presented of local treatments including dates of treatment, time between the diagnosis of metastatic renal cell carcinoma and local treatment and sites exposed.

- Radiological assessment of the CR:
 - Disappearance of all known target lesions (Yes/No);
 - Disappearance of all non-target lesions (Yes/No);
 - No new lesions (Yes/No);

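### The primary objective seeks factors associated with CR, but only unadjusted one-variable comparisons are planned, so a characteristic's own association cannot be separated from that of related ones

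*SAP*

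**What the plan says.** SAP 2.2.1 sets the primary objective: describe Cases, compare them with Controls, and do so "to identify factors associated with the occurrence of CR".

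The methods are in SAP 4.1. For continuous variables: "Quantitative parameters will be compared between groups using the following methods", followed by a t-test, or a Wilcoxon test with the Hodges-Lehmann estimate. Nominal variables get chi-square or Fisher tests. Ordinal variables get a Cochran-Mantel-Haenszel row-mean-score test with no stratification factor named, so it adjusts for nothing. Protocol 8.8 lists the same kind of tests.

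SAP 6.3.1 and 6.3.2 apply these tests to each characteristic in turn. Four starred variables (nephrectomy, necrosis, embolism, sarcomatoid component) also get an odds ratio: "For these qualitative variables, the odds ratio (Case versus Control) will be presented". The table shells in Annex 1 have room for one p-value and one crude difference or odds ratio per variable.

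Neither document has a regression model for CR, a covariate list, a stratified comparison or matching. SAP 2.4 sends only biological data and biomarkers to a separate plan, so that plan does not cover the clinical characteristics.

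**The concern.** Many of the characteristics tested separately are related. Some are linked by construction: the number of metastatic sites and each individual site; lymph nodes and their two sub-locations; T, N and M and the combined TNM. Others share prognostic content: protocol Appendix 8 lists the number of metastatic sites and the interval from diagnosis to systemic treatment among the prognostic factors, and SAP 6.3.2 tests each of them alone beside MSKCC class.

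The groups also differ by design. Controls must meet life-expectancy and laboratory limits and have had no previous systemic treatment (protocol 8.2.4); Cases need not (8.2.3). Every participating physician may enter Cases, while five teams are named for Controls (8.2.1).

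A crude difference may therefore reflect the characteristic itself, a related characteristic, or selection. At stake is how the list of differences is read: physicians could take several correlated markers of good prognosis for separate pointers to CR.

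**Working it through.** **1. The plan's own power figure.** Inputs from SAP 2.5 and 4.1: 40 Cases, 80 Controls, two-sided 5%, d = 0.55.

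- Normal approximation: 0.55 × √(40 × 80 / 120) = 2.840; 2.840 − 1.960 = 0.880, so power is 81.1%. The noncentral t gives 80.4%, and exactly 80% at d = 0.547.
- Odds-ratio table, for example 50% in Controls and OR 3.44: Case frequency = 3.44 / 4.44 = 0.775, power 84.6%. Over the whole table the range is 79.8% to 84.7%.

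The stated power reproduces. It is power for a single unadjusted comparison.

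**2. MSKCC-driven scenarios.** The documents give no MSKCC distribution and no site count by class, so all inputs here are assumptions. Only MSKCC class is related to CR; having two or more sites depends on class alone. Controls are 30/50/20% good/intermediate/poor.

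Worked case, with Cases 50/42/8% and two or more sites in 30/55/80% by class:

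- Controls: 0.30 × 0.30 + 0.50 × 0.55 + 0.20 × 0.80 = 0.525
- Cases: 0.50 × 0.30 + 0.42 × 0.55 + 0.08 × 0.80 = 0.445
- Crude OR = (0.445 / 0.555) / (0.525 / 0.475) = 0.73, with no effect of sites within class.

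| Cases by MSKCC | Two or more sites by class | Crude chi-square flags sites |
|---|---|---|
| 50/42/8% | 30/55/80% | about 12% |
| 50/42/8% | 40/55/70% | about 7% |
| 50/42/8% | 45/55/65% | about 6% |
| 40/46/14% | 30/55/80% | about 6% |
| 40/46/14% | 40/55/70% | about 5% |

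In the first row, repeated simulations gave 11.8% to 12.7% crude and 4.8% to 5.7% with a Mantel-Haenszel test stratified by MSKCC.

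**3. Correlated continuous characteristics.** Again assumed: A truly differs by d; B has no association with CR once A is known, and correlates ρ with A within groups. The crude difference in B is then ρ × d. For d = 0.55 this is 0.165, 0.275 and 0.385 at ρ = 0.3, 0.5 and 0.7.

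| d for A | ρ | B flagged by t-test (noncentral t) | Same, 3,000 simulations | B flagged in logistic model with A and B |
|---|---|---|---|---|
| 0.55 | 0.3 | 13.5% | 14.5% | 5.1% |
| 0.55 | 0.5 | 29.1% | 31.9% | 4.4% |
| 0.55 | 0.7 | 50.5% | 50.5% | 5.0% |
| 0.80 | 0.3 | 23.3% | 24.4% | 4.9% |
| 0.80 | 0.5 | 53.5% | 54.1% | 4.7% |
| 0.80 | 0.7 | 81.8% | 82.4% | 5.6% |

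**4. Cost of adjusting.** If a factor correlates ρ with the other covariates, its variance is inflated by 1 / (1 − ρ²). Power at d = 0.55 is Φ(2.840 × √(1 − ρ²) − 1.960), and the d detectable with 80% power is 0.547 / √(1 − ρ²).

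| ρ | Power at d = 0.55 | Detectable d |
|---|---|---|
| 0 | 81% | 0.55 |
| 0.3 | 77% | 0.57 |
| 0.5 | 69% | 0.63 |
| 0.7 | 53% | 0.77 |

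**5. How large a model 40 Cases can carry.** Age, number of sites, nephrectomy and clear-cell histology take 1 df each. MSKCC takes 1 as a linear score (total 5, or 40 / 5 = 8 Cases per parameter) or 2 as three classes (total 6, or 6.7 per parameter). With 8% poor-risk Cases, as assumed above, that class holds about 0.08 × 40 ≈ 3 Cases. Both figures favour a short list and penalised estimation.

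**The case against.** The strongest defence is that objective, sample size and tests agree with one another. The objective speaks of associated factors, not independent ones; the power statement covers one unadjusted comparison at a time; and the planned tests deliver description, comparison and marginal association. That stands. A reader might infer that the study cannot answer its primary question, or that each significant variable will be reported as an independent factor. The documents support neither: the descriptive and comparative parts are met, and the SAP has no rule for calling a variable a factor.

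The size is also open to challenge. The MSKCC results run from nominal to about 12% on modest changes to assumed inputs, and the larger figures need assumed correlations of up to 0.7. No single inflation figure can be defended. The simulations used a stratified test and an ordinary two-covariate logistic model, so they show what adjustment does in principle, not how a Firth model would perform here.

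Finally, adjustment for a few covariates does not remove the differences in eligibility, so adjusted odds ratios would not be clean independent effects either. That also stands, and should be said in the report. None of it supplies the missing adjusted analysis.

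**Conclusion.** The concern holds as a limit on interpretation. As planned, the comparisons between unmatched groups show which characteristics differ. They cannot show whether a characteristic has its own association with CR or only accompanies related ones such as MSKCC class or number of sites.

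The size rests on assumptions. A characteristic with no independent association is flagged in about 5% to 12% of studies in the MSKCC-driven scenarios, and in about 13% to 50% (15% to 50% in the 3,000-run simulation) when it correlates 0.3 to 0.7 with a true factor of d = 0.55. After adjustment the figure is about 5%. The range runs from negligible to large, and the documents do not say where this study lies. The point concerns clinical characteristics only. The change should be made because it is cheap and the covariates are already collected.

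**What to change.** Before database freeze, add to SAP 6.3.2 one pre-named Firth-penalised logistic model, Case versus Control, reporting adjusted odds ratios with 95% profile-likelihood intervals. Covariates:

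- age at Sunitinib start, from the birth and start dates on both case report forms. SAP 5.2 takes age at inclusion, which for Cases can be up to 5 years after CR but for Controls is before treatment, so it is not comparable between groups;
- MSKCC class, as a linear score (5 df in total) or three categories (6 df), chosen in advance;
- number of metastatic sites;
- nephrectomy;
- clear-cell histology.

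With it:

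- First reconcile the MSKCC label. The forms in protocol Appendices 5 and 6 print the class with more than two adverse factors as good, while SAP 6.3.2 has a poor-prognosis class. Check how sites recorded it.
- Keep the crude tests, labelled unadjusted and exploratory.
- Give a same-centre comparison descriptively, and only if enough Cases remain. If 40 Cases were spread evenly over 20 sites (an assumption), five centres would hold 5 × 2 = 10.
- State that the 80% power applies to single unadjusted comparisons, with the loss shown in step 4 of the working, and that adjustment does not remove the eligibility differences.

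If the sponsor declines the model, the minimum is to restate the objective as exploratory, unadjusted association.

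The cost is a short SAP addition and its code, wider intervals with 40 Cases, and some patients lost to missing covariates, since SAP 5.1 in general does not replace missing values.

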8.8. Data analysis

A detailed statistical analysis plan (SAP) will be written and will constitute the frame of reference with regards to statistical analyses. **This analysis plan will be validated by the scientific committee and the study sponsor and will focus primarily on defining the populations studied as well as the statistical methods used.** Any modification of the statistical methods described in the SAP should be reported and documented in the clinical/statistical report.

Interim analysis

An interim analysis, based on the descriptive analysis of the patients included and on the data collected, will be performed during the study. This analysis will be performed as soon as 20 patients presenting a complete response (cases) have been included and followed for 6 months.

Statistics

For the case and control groups, the quantitative data will be described by their population sizes, means, standard deviations, confidence intervals, medians and outlying values. The qualitative data will be described by their frequencies and percentages (95% bilateral confidence intervals will be provided where relevant). The number of missing data will also be recorded.

All of the characteristics of the variables collected from cases and controls will be compared by the Student's t test for Gaussian quantitative data, the Mann-Whitney test for non-Gaussian quantitative data and the chi-squared test for qualitative data. The threshold of bilateral significance is set at 5%.

Data will be analyzed using SAS software (version 9.1 - SAS Institute, North Carolina, USA).

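### SAP 4.1 names Student's t-test without an unequal-variance option; at 40 v 80 its p-values and 95% CIs can miss their nominal levels if the group SDs differ

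*SAP*

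**What the plan says.** SAP 4.1 sets a two-step rule for quantitative characteristics. First, "the distribution of the parameter will be checked graphically and by using Skewness and Kurtosis and Shapiro-Wilk statistics". If the variable is judged normal, "groups will be compared using a Student's t-test and the difference in means and the 95% Confidence Interval (CI) will be presented". If not, "groups will be compared using a Wilcoxon rank sum test and Hodges-Lehmann estimator, with a presentation of the 95% CI". The level is set by "Statistical tests will be carried out bilaterally at a 5% significance level (alpha)".

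Protocol 8.8 has the same structure: variables are "compared by the Student's t test for Gaussian quantitative data, the Mann-Whitney test for non-Gaussian quantitative data". The model table in SAP Annex 1 labels the p-value with a Student's t footnote.

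Neither document mentions equal or pooled variance, Welch or Satterthwaite, or says what to do if the group SDs differ. On size, SAP 2.5 states: "A sample size of N = 40 cases and N = 80 controls will provide a power of 80% in the detection" of Cohen's d of at least 0.55 for a normally distributed variable. That is a standardised effect with one common SD. No SD is given for any characteristic.

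**The concern.** Student's t-test estimates one common variance from both groups. With equal group sizes it tolerates unequal variances well. With 1:2 sizes it does not, because the larger group dominates the pooled estimate while the smaller group dominates the true sampling error of the difference. If the 40 Cases are the more variable group, the standard error is too small, p-values are too low and intervals too narrow. If they are the less variable group, the reverse holds and power is lost.

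These comparisons serve the primary objective, which is to identify factors associated with complete remission. The quantitative variables listed in SAP 6.3 are age, height, weight, tumour size, time since metastatic diagnosis, time from that diagnosis to nephrectomy and to Sunitinib start, and the number of metastatic sites. Any of these judged normal would be reported with a t-test p-value and a 95% CI for the mean difference.

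The two groups also enter under different criteria. Cases may have reached remission at any time in the preceding 5 years. Controls are starting Sunitinib and must meet laboratory and life-expectancy limits. Equal spread therefore cannot be taken for granted.

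**Working it through.** **Inputs from the documents.** 40 Cases and 80 Controls; two-sided 5%; d = 0.55 with 80% power (SAP 2.5 and 4.1).

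**Assumption.** The ratio r = SD(Cases)/SD(Controls), taken from 0.5 to 2 because the documents give no SDs. The Control SD is set to 1.

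**Step 1: the plan's own figure.** The noncentrality is 0.55/√(1/40 + 1/80) = 0.55/√0.0375 = 2.84. On 118 df the equal-variance t-test has 80.4% power, and the smallest d with 80% power is 0.547. The stated figure reproduces.

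**Step 2: what the pooled test estimates.**

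- True variance of the mean difference: V = r²/40 + 1/80.
- Expected pooled estimate: P = [(39r² + 79)/118] × 0.0375.
- Approximate true type I error: 2 × [1 − Φ(1.96 × √(P/V))].

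Worked for r = 2: V = 4/40 + 1/80 = 0.1125. P = (156 + 79)/118 × 0.0375 = 0.0747. √(P/V) = 0.815, and 1.96 × 0.815 = 1.597, so the error is about 11%.

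**Step 3: simulation check.** 400,000 normal data sets per ratio at 40 v 80, no true difference:

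| r (Case/Control SD) | V | P | √(P/V) | Student, simulated type I error | Coverage of its 95% CI | Welch, simulated type I error |
|---|---|---|---|---|---|---|
| 0.5 | 0.0188 | 0.0282 | 1.23 | 1.7% | 98.3% | 5.0% |
| 0.8 | 0.0285 | 0.0330 | 1.08 | 3.5% | 96.5% | 5.0% |
| 1.0 | 0.0375 | 0.0375 | 1.00 | 5.0% | 95.0% | 5.0% |
| 1.25 | 0.0516 | 0.0445 | 0.93 | 6.9% | 93.1% | 5.0% |
| 1.5 | 0.0688 | 0.0530 | 0.88 | 8.5% | 91.5% | 5.0% |
| 2.0 | 0.1125 | 0.0747 | 0.81 | 11.0% | 89.0% | 5.0% |

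Coverage is 100% minus the type I error.

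**Step 4: is the allocation the cause?** Repeating the runs at 60 v 60, Student's test stays between 5.0% and 5.1% at every ratio. The 1:2 split drives the distortion.

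**Step 5: what the alternative costs.** With equal variances and d = 0.55, Welch has 80.0% power against 80.4% for Student in these runs, a loss of about 0.4 points. Other runs gave 0.3.

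**Step 6: would a variance pre-test do as well?** Choosing between the two tests by a folded F test gave true levels of 4.3% to 5.8% over the same ratios. Welch alone stayed at 5.0%, so the pre-test adds nothing.

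**The case against.** The strongest reply is that the point is small and rests on SD ratios that nobody has shown. Most of it stands:

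- **No SDs.** For ratios of 0.8 to 1.25 the true level stays within about 2 points of 5%. Nothing in the documents shows that any characteristic has a ratio of 1.5 or 2.
- **Narrow scope.** Most characteristics in SAP 6.3 are categorical. Among the quantitative ones, time intervals and tumour size are often skewed, and non-normal variables go to the Wilcoxon test. The t-test may in practice be used for age, height and perhaps weight.
- **The normality step intervenes.** If normality is checked on all 120 patients together (the SAP does not say whether overall or by group), a large SD difference itself looks non-normal. At ratio 2, Shapiro-Wilk alone sent about 52% of simulated data sets to Wilcoxon, and the two-step error was about 8.8% rather than 11%. Checking within groups would not give this reduction.
- **Wilcoxon is not immune.** It reached about 8.4% at ratio 2, so changing the t-test does not cure every effect of unequal spread.
- **SDs are reported by group**, so a large imbalance would be visible to a reader.

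One further argument is that the SAP never says pooled, so Welch might be what is meant. That does not remove the point. Student's t-test named without qualification is ordinarily the equal-variance test. If it is not meant so here, the choice between two p-values and two intervals is left open until the data are seen. The same sentence settles both cases.

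**Conclusion.** The point holds as a cheap improvement of minor severity. Under the ordinary reading of Student's t-test, the planned test and CI can miss 5% and 95% at 40 v 80 when the group SDs differ. The shift is modest for SD ratios of 0.8 to 1.25 (3.5% to 6.9%) and material only for larger assumed ratios (8.5% at 1.5, 11.0% at 2, 1.7% at 0.5). These figures assume normal data and that the t-test is always the one applied.

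Three stronger readings are tempting, and the documents do not support them:

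- **That results will be wrong whenever the variances differ.** Small differences in SD do little, and with no SDs given no actual error can be shown.
- **That Cases are probably the more variable group, so the test is anti-conservative.** The laboratory and life-expectancy limits on Controls do not concern the variables compared in SAP 6.3. Cases are themselves selected by a rare outcome confirmed on central scan review, so they could equally be the more homogeneous group. The direction cannot be known in advance.
- **That the sample size is in error.** The 80% power at d = 0.55 reproduces.

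**What to change.** In SAP 4.1, state that variables judged normal are compared with the Welch (Satterthwaite) unequal-variance t-test, and that the 95% CI of the mean difference comes from the same method. Make the same change in protocol 8.8 and in the Student's t footnote of the SAP Annex 1 model table. Do not add a preliminary test of variances.

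The cost is a wording change in three places, with no new data and no change to design or sample size. If the variances are equal, power at d = 0.55 falls by about 0.3 to 0.4 percentage points (from 80.4% to 80.0% in the runs above).
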